7.2 STUDY RELATED AE DEFINITION

This section applies particularly to the Phase 2 part of the study. The transurethral intervention with a rigid scope similar in size to the Rezūm device commonly is associated with transient symptoms. For the purpose of this study, these types of transient symptoms will not be considered an adverse event. The corollary to a surgical procedure is bleeding. Bleeding will occur in all surgical BPH procedures, and bleeding, therefore, is not clinically significant and typically not reported as an AE. The following types of signs and symptoms that are attributed to the procedure, last less than or equal to 72 hours, AND do not result in intervention, re-hospitalization, or prolonged unplanned hospitalization, will not be considered AEs.

- Dysuria
- Hematuria
- Storage (irritative) LUTS
- Urgency/frequency
- Nocturia
- Urge incontinence
- Voiding (obstructive) LUTS
- Hesitancy
- Decrease flow
- Increase residual
- Pain/discomfort
- Catheterization

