7 ADVERSE EVENTS

7.1 DEFINITION OF ADVERSE EVENT(S)

For the purpose of this protocol, an “adverse event” (AE) will be defined as any adverse medical condition change (i.e., *de novo* or increased severity in a preexisting condition) from the subject’s baseline condition that occurs during the course of the clinical study, after starting study procedure, whether considered procedure-related or not. Therefore, conditions existing at the time of enrollment will not be reported as an AE unless the event increased in clinically significant severity during the course of the study. Events which resolve and then recur should be reported as separate AEs. Events that are a continuation of an unresolved AE should not be reported as a new AE but a continuation of the previously reported AE.

The reason for catheterization will not be considered an AE if catheterization occurs and ends within 72 hours after the procedure because this is generally considered standard of care to allow the tissue to heal.

The reason for catheterization will be considered an adverse event if the following applies:

- a. If catheterization occurs within a 72-hour window after the procedure and the duration of catheterization extends beyond that 72-hour window
- b. If catheterization occurs outside of a 72-hour window after the procedure
- c. If catheterization recurs after the same symptom is resolved

Lower Urinary Tract Symptoms (LUTS) will not be considered an adverse event if LUTS occurs and ends within a 3-day window (72 hours) after the procedure.

Lower Urinary Tract Symptoms (LUTS) will be considered an adverse event if the following applies:

- a. If LUTS occurs within a 3-day window (72 hours) after the procedure and the duration of LUTS extends beyond that 3-day window (72 hours)
- b. If LUTS occurs outside of a 3-day window (72 hours) after the procedure
- c. If LUTS recurs after the same symptom is resolved

Normally expected symptoms caused by the treatment will not be considered AEs for this study. For example, normal pain or minor bruising at the surgical site due to the healing of the site will not be considered an AE. “Treatment” includes all procedures and treatments administered according this protocol.

An AE may be volunteered spontaneously by the subject or discovered as a result of questioning or by physical examination by the investigator.

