14.2 STATISTICAL ANALYSIS

Descriptive statistics will be calculated and reported for study variables, as appropriate. Continuous variables (e.g., symptom score, uroflowmetry, quality of life assessments) will be summarized using statistics such as means, standard deviations and absolute change from baseline. Categorical variables (e.g., adverse events) will be summarized as frequency

distributions. Adverse events and technical observations will be reported by frequency of occurrence, severity and relationship to the vapor treatment device.

All subjects enrolled in this study (including those withdrawn from the study or lost to follow-up) will be accounted for and documented.

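### Section 7.2 limits how long an exempt symptom lasts but not when it starts, so it contradicts 7.1 on late LUTS and drops late, short, procedure-attributed hematuria or pain from the AE table

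*Combined protocol and SAP*

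**What the plan says.** Section 7.2 is directed mainly at Phase 2. Its stated reason is that passing a rigid scope of this size "commonly is associated with transient symptoms". It then exempts listed signs and symptoms that are "attributed to the procedure, last less than or equal to 72 hours, AND do not result in intervention"; the remaining conditions finish the sentence: "re-hospitalization, or prolonged unplanned hospitalization, will not be considered AEs". The list includes dysuria, hematuria, storage and voiding LUTS, "Pain/discomfort" and catheterization. Just before the list, 7.2 adds: "Bleeding will occur in all surgical BPH procedures, and bleeding, therefore, is not clinically significant and typically not reported as an AE".

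Section 7.1 handles timing differently. For LUTS and for the reason for catheterization, it ties the 72 hours to the procedure and lists what counts as an AE, including, at (b), "If LUTS occurs outside of a 3-day window (72 hours) after the procedure", and at (c), recurrence after resolution. Its general rule on recurrence is "Events which resolve and then recur should be reported as separate AEs". It also excludes normally expected symptoms of the treatment, with ordinary healing pain as an example and no time limit.

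Section 14.2 states the analysis that these definitions feed: "Adverse events and technical observations will be reported by frequency of occurrence, severity and relationship to the vapor treatment device".

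**The concern.** The exemption appears meant for short-lived effects of instrumentation, but its operative test is the length of the episode. Nothing in the sentence requires the episode to begin near the procedure, so the exemption stays open for as long as subjects are followed, up to 5 years.

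Two things follow. First, 7.1 and 7.2 give opposite answers for the same late, short LUTS episode, and the investigator has no rule for choosing between them. Second, the exemption reaches only events attributed to the procedure. A late, short episode of hematuria is therefore kept if judged unrelated and lost if judged related. Documenting safety and post-operative effects is a Phase 2 objective (5.1), and a table by relationship that omits related events by definition will understate the device's share.

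**Working it through.** The plan states no figure on this point, so the check applies the text of 7.1 and 7.2 to each kind of episode. Each is taken to be new or worse than baseline and, unless noted, attributed to the procedure. Untreated means no intervention, re-hospitalization or prolonged unplanned hospitalization.

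| Episode | Section 7.1 | Section 7.2 | Result |
|---|---|---|---|
| LUTS, starts and ends within 72 h of procedure, untreated, no recurrence | Not an AE | Not an AE | Sections agree |
| LUTS, starts after 72 h, lasts at most 72 h, untreated | AE under (b) | Not an AE | Contradiction |
| Hematuria or pain, starts after 72 h, lasts at most 72 h, untreated | No specific timing rule | Not an AE | Not an AE |
| The same hematuria or pain, judged unrelated | AE under the general definition | Exemption does not apply | AE |
| Hematuria or pain lasting over 72 h | AE unless judged normally expected | Exemption does not apply | Reportable, subject to that exclusion |
| Any listed symptom leading to intervention, re-hospitalization or prolonged unplanned hospitalization | General definition applies | Exemption does not apply | 7.2 does not remove it |
| Recurrent short, late hematuria or pain | Recurrences reported as separate AEs | Each episode alone would pass the test | Ambiguous |

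**Dysuria.** The 7.2 list places it apart from the LUTS entries, which puts it with hematuria and pain. An investigator who classes it as LUTS would apply 7.1(b) and (c) instead.

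**Catheterization.** It appears in both sections, but a catheter may itself count as an intervention and so fail the 7.2 test. LUTS is the cleaner contradiction.

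**Attribution.** The third and fourth rows differ only in the investigator's causality judgment. Section 7.7 has five relationship grades, and 7.2 does not say which of them count as attributed.

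**Other capture.** No scheduled follow-up item in Tables 6-1 and 6-2 measures hematuria, and no urinalysis is scheduled after baseline. Pain is assessed at scheduled visits, but the scale in 14.8.14 records pain at that moment, so an episode between visits can be missed.

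**Scale.** Phase 2 enrolls up to 15 subjects. One subject whose only episode of a given kind is omitted changes the per-subject rate of that event by 1/15 = 0.067, or 6.7 percentage points, and by more if fewer than 15 are treated. How often this would happen cannot be derived from the documents.

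**The case against.** The strongest reply is that the two sections should be read together. Section 7.2 opens with transient effects of the scope, and 7.1, immediately before it, counts the same 72 hours from the procedure. On that view the peri-procedural window is the natural meaning and only the drafting is loose. This is a fair guess at intent, but the sentence that decides reportability states no window. Section 7.1 does state one, and 7.2.1 gives its own limit of 3 months for sexual side effects.

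A reader might infer that late procedure-related symptoms can never become AEs. The text does not support that: episodes over 72 hours, or leading to intervention or hospitalization, lose the 7.2 exemption. In addition, 7.1 asks for events to be classified by underlying cause, so a symptom traced to stricture or prostatitis, for example, is recorded under a diagnosis that is not on the exempt list.

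A reader might also infer that a relapsing symptom yields no AEs because each short recurrence passes the 72-hour test. That needs each recurrence to be given a fresh allowance, which no passage says; the general recurrence sentence in 7.1 literally directs reporting. The other reading is not absurd, since if that sentence already overrode the exemptions, item (c) for LUTS and for catheterization would be redundant. The point stands only as an ambiguity.

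Finally, Figure 7-1, the AE determination flowchart, was not available for this check and may carry a timing test. The finding rests on the written text.

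**Conclusion.** The concern holds in limited form. As written, 7.2 contradicts 7.1(b) on late, short LUTS. It also removes late, short, untreated hematuria or pain (and dysuria, if not classed as LUTS) when these are attributed to the procedure, while identical unrelated episodes remain. The omission falls on the related categories of the 14.2 table. The treatment of recurrent short episodes is unclear rather than wrong.

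The effect on the reported rates cannot be estimated, because it depends on how often such episodes occur; the 6.7-point figure is the least that one omitted subject would cost, not a forecast. The conclusion assumes a literal reading of 7.2 and that Figure 7-1 adds no onset window. It is a defect in the reporting definition that should be corrected. It does not show that safety data are lost wholesale over 5 years.

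**What to change.** In 7.2, replace the duration clause with: *start and end within 72 hours after the procedure and do not recur*. This matches 7.1 and keeps the exemption for instrumentation effects. Apply the same window to two other statements that have none, or the gap remains for the symptoms concerned: the bleeding statement in 7.2 and the exclusion of normally expected symptoms in 7.1. Keep the 7.1 rule that recurrences are reported as separate AEs, and check that Figure 7-1 agrees with the revised text.

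The difference in treatment between related and unrelated episodes would then be confined to the first 72 hours, where it is deliberate. The cost is a somewhat higher count of mild AEs, including healing pain or bleeding that continues past 72 hours. The change concerns reporting only and leaves treatment, visits and sample size as they are.

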7.2.1 Erectile Dysfunction and Retrograde Ejaculation

Erectile dysfunction (ED) is commonly present in this population group. Therefore, only *de novo* ED and retrograde ejaculation attributable to the procedure within the first 3 months will be considered an AE. ED is a progressive disease and is expected to increase in frequency with age regardless of the procedure.

7.3 ANTICIPATED ADVERSE EVENT(S)

Anticipated adverse device events are those that may be reasonably expected to occur in association with a surgical BPH procedure, and include those listed here or reported in the literature associated with a minimally invasive BPH ablation procedure:

- Pain
- Bleeding
- Infection / fever

- **Perforation**
- **Retrograde ejaculation**
- **Urinary symptoms including:**
- **Dysuria**
- **Frequency**
- **Urgency**
- **Nocturia**
- **Urinary retention**
- **Temporary acute incontinence**
- **Sensation of not emptying bladder completely**
- **Transient incontinence**
- **Urethral stricture**
- **Urethritis**
- **Irritative urinary symptom**
- **Urethral injury**
- **Urinary clot retention**
- **Chronic pain at site**
- **Bladder spasm**
- **Rectal, perianal findings**
- **Anal irritation**
- **Flu-like symptoms**
- **Hemospermia**
- **Epididymitis**
- **Blood pressure change during therapy**
- **Flank pain**
- **Blood loss (> 50 ml)**
- **Bowel irritation**
- **Erectile dysfunction**
- **Retrograde ejaculation**
- **Pressure sensation**
- **Prostatitis**

7.4 SERIOUS ADVERSE EVENT(S)

An AE is considered to be serious if it:

- **Results in death (as part of any surgical procedure there is a chance of this SAE);**
- **Is life threatening;**
- **Requires subject hospitalization or prolongation of existing hospitalization;**
- **Results in persistent or significant disability/incapacity;**
- **Is considered an important medical event**
-

Important medical events that may not meet one of the above definitions could be considered SAEs if they jeopardize the health of the subject, or require surgical intervention to prevent one of the outcomes listed in the above definition. Serious adverse events may or may not be related to the Rezūm procedure.

7.5 UNANTICIPATED ADVERSE DEVICE EFFECT(S) (UADE)

An unanticipated adverse device effect is any serious adverse effect on health or safety or any life threatening problem or death caused by, or associated with, a device, if that effect, problem, or death was not previously identified in nature, severity, or degree of incidence in the "investigational plan" or application (including a supplementary plan or application), or any other unanticipated serious problem associated with a device that relates to the rights, safety, or welfare of subjects.

7.6 REPORTING OF ALL ADVERSE EVENTS

All AEs that occur to any subject during the study must be documented on the Adverse Event CRF, including the following information: event description, treatments given, intensity of the event, relationship with the device, and the outcome of the event.

If the Principal Investigator determines that an AE is a SAE or a UADE, all as defined in this protocol, it is to be reported to the Sponsor as soon as possible but no later than 10 working days after the Principal Investigator first learns of the incident. The Sponsor will investigate any reported SAE or UADE to determine if the event type and severity was anticipated in the investigational plan.

Investigators are required to report all UADEs to the reviewing ethics committee (EC) no later than 10 working days from the date that the Principal Investigator first became aware of such UADE. In addition, the Principal Investigator must comply with any other reporting requirements of the reviewing EC.

A Sponsor who conducts an evaluation of a UADE shall report to all reviewing EC's and participating Investigators within 10 working days after the Sponsor first receives notice of the effect.

The Sponsor also must take the appropriate action regarding termination of the study when it is determined that an AE presents an unreasonable risk to subjects. Any such termination must occur no later than 15 working days from receipt of notice of the adverse event.

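### The sponsor's event evaluation in 7.6 omits the incidence limb of the UADE definition in 7.5, and 7.3 gives no reference rate, so an excess of serious listed events could be missed

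*Combined protocol and SAP*

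**What the plan says.** **Definition (7.5).** A serious effect, life-threatening problem or death associated with the device is a UADE if it "was not previously identified in nature, severity, or degree of incidence" in the investigational plan or application. A catch-all follows: "or any other unanticipated serious problem associated with a device that relates to the rights, safety, or welfare of subjects".

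**Sponsor's evaluation (7.6).** The sponsor investigates every reported SAE or UADE "to determine if the event type and severity was anticipated in the investigational plan". Incidence is not named, and neither is the application.

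**Investigator's role (7.6).** The investigator classifies first, under the protocol's definitions: "If the Principal Investigator determines that an AE is a SAE or a UADE, all as defined in this protocol". There is a direct route onward: "Investigators are required to report all UADEs to the reviewing ethics committee (EC) no later than 10 working days".

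**Reference list (7.3).** Anticipated events "include those listed here or reported in the literature associated with a minimally invasive BPH ablation procedure". No term carries an expected incidence or a grade from the severity scale in 7.8. The only qualifiers are a lower bound on blood loss (more than 50 ml) and duration words such as temporary, transient and chronic. No literature source is cited.

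**Analysis (14.2).** Adverse events are summarised descriptively by frequency, severity and relationship to the device, with no benchmark.

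**The concern.** The protocol contains two tests for the same decision, and the one given to the sponsor is narrower than the definition. A serious event of a listed type and familiar severity passes the 7.6 check however often it occurs, although 7.5 says that an unforeseen frequency is enough to make it a UADE. The classification has a consequence: the sponsor's own 10-working-day report to ethics committees and investigators in 7.6 is tied to UADEs.

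Frequency is a relevant signal in this study. Section 1 says that the study uses a revised version of a system tested earlier in people. Section 5.2 allows power from 175 W to 250 W and water flow from 2.7 to 5.0 ml/min, and it uses higher caloric treatments in later subjects if they are tolerated. If the higher settings cause harm, one plausible form is more events of kinds already on the list, such as perforation, urethral injury or urethral stricture. The incidence limb is the part of 7.5 that addresses this.

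**Working it through.** **Step 1: the tests side by side.**

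| Element | 7.5 definition | 7.6 sponsor evaluation | Reference given in 7.3 |
|---|---|---|---|
| Nature or type | yes | yes | list, plus uncited literature on minimally invasive BPH ablation |
| Severity | yes | yes | no grade; one blood-loss bound and some duration words |
| Degree of incidence | yes | no | none |
| Compared against | plan or application | plan only | not applicable |

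The third row is the contradiction. The second and third rows show that, even where a test is named, there is little to compare an event with.

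**Step 2: what follows.** Take several serious events of one listed type. Under 7.6 and 7.3 the type is on the list and no severity level is exceeded because none is set, so the sponsor can call them anticipated at any count. Under 7.5 the question of incidence remains open. Read strictly, since 7.3 identifies no incidence, even a single serious listed device effect might count as not previously identified in that respect. The same events can thus be classified in opposite ways.

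**Step 3: why a reference rate is needed (illustration only).** The documents state no expected rate, so there is no plan figure to reproduce. Inputs: n = 15, the Phase 2 maximum in 5.2; p, the true rate of one type of serious event, is an **assumption**, shown over a range. Events are taken as independent between subjects.

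Formula: P(X ≥ r) = 1 − Σ C(15, k) p^k (1 − p)^(15 − k), summed over k = 0 to r − 1.

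Example, p = 0.05 and r = 3: 1 − (0.4633 + 0.3658 + 0.1348) = 0.036.
Example, p = 0.10 and r = 3: 1 − (0.2059 + 0.3432 + 0.2669) = 0.184.

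| Assumed rate | P(2 or more of 15) | P(3 or more of 15) | Smallest count with upper tail ≤ 5% |
|---|---|---|---|
| 1% | 1.0% | 0.04% | 2 |
| 2% | 3.5% | 0.3% | 2 |
| 5% | 17.1% | 3.6% | 3 |
| 10% | 45.1% | 18.4% | 5 |
| 20% | 83.3% | 60.2% | 7 |

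Three events in 15 would be remarkable at 2% and ordinary at 20%. Without an expected rate, neither the sponsor nor the investigator can apply the incidence limb consistently.

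**The case against.** The strongest reply is that 7.5 is the protocol's only definition of a UADE and that it is intact. The investigator classifies under it, incidence included, and reports UADEs to the ethics committee without waiting for the sponsor. The study has one centre, so that investigator sees every event. The catch-all in 7.5 adds further cover, and the phrase in 7.6 may be mere shorthand.

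Most of this stands, and it rules out several stronger readings that a reader might infer:

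- **That an excess of listed events can never become a UADE.** The investigator's duty under 7.5 does not depend on the sponsor's check.
- **That this is the only safety trigger.** Section 7.6 requires the sponsor to act on termination when any adverse event presents an unreasonable risk, UADE or not. Section 5.2 moves later subjects to a lower caloric treatment if one is not tolerated.
- **That SAEs which are not UADEs never reach the ethics committee.** Section 7.6 binds the investigator to the committee's other reporting requirements, and 13.1 lets stricter requirements prevail. Those requirements are not in the documents.
- **That any published event counts as anticipated.** Section 7.3 limits the literature to minimally invasive BPH ablation procedures.
- **That the remark in 7.4, "Results in death (as part of any surgical procedure there is a chance of this SAE", makes a death anticipated.** It sits in the SAE definition, death is not on the 7.3 list, and 7.5 names death as a possible UADE.

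The reply does not remove the mismatch. The clause in 7.6 is the protocol's only description of what the sponsor's evaluation decides, and it covers less than the definition. The investigator has no expected incidence to work from either. The application mentioned in 7.5 might contain rates, but it is not among the documents, and 7.6 does not direct the sponsor to it.

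**Conclusion.** The point holds as an inconsistency with a practical consequence. The sponsor's evaluation in 7.6 is narrower than the definition in 7.5, and 7.3 supplies no expected incidence, no severity grade and no literature source. The sponsor can therefore pass an excess of serious listed events as anticipated when 7.5 would make it a UADE. The excess could be missed at that step; other protections remain, and the documents do not support saying that it must be missed.

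The textual finding needs no assumption. Its size cannot be fixed from the documents: the chance of three or more events in 15 runs from 0.3% to about 60% as the assumed rate goes from 2% to 20%. No particular count can therefore be called a clear excess on what the plan states. That range is the reason for stating a reference rate; it does not measure harm.

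**What to change.** **Main change, 7.6.** Replace the type-and-severity test with the three limbs of 7.5, applied to the same references and to accumulated events. Suggested text: *The sponsor will investigate each reported SAE or UADE and, considering all such events to date in treated subjects, will determine whether its nature, severity, or degree of incidence had been identified beforehand in the plan or the application.*

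**Supporting changes, 7.3.** Either limit the anticipated events to the listed terms or cite the literature relied on. Beside each term, state the expected incidence and severity with their source where the sponsor has them, and say so where it has none. The earlier human study in Section 1 (four acute and nine chronic subjects) is one possible source, but it is small and used an earlier version of the system.

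No numerical trigger is proposed, because the documents give no rate on which to base one.

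**Cost.** One sentence in 7.6 and added information in 7.3, with some work to assemble sources. Treatment, sample size and visits do not change. The downside is that a few more events may be reported to the ethics committee.
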